### *Pharmacokinetics*

Absorption: Bioavailability was 46% (90 CI 40-53%) in healthy subjects. A high-fat meal had no effect on cobimetinib AUC and Cmax after a single 20 mg cobimetinib dose in healthy subjects.

Distribution: 95% bound to human plasma proteins. Vd 806 L.

Metabolism: CYP3A oxidation and UGT2B7 glucuronidation.

Half-life, elimination: 44 hours (range 23-70).

Time to peak: Median time to Tmax 2.4 (range 1-24) hours.

Excretion: Feces (76%; ~7 as unchanged drug); Urine (~18%; ~2% as unchanged drug)

### *Adverse events*

See CAEPR in [Section 9.5.2](#).

*Nursing guidelines*

- Agent can cause decreased LVEF function. Instruct patients to report any lower extremity swelling, shortness of breath, and/or chest pain to study team.
- Diarrhea and other gastrointestinal side effects are common. Treat symptomatically and monitor for effectiveness of intervention.
- Rash is common and is usually acneiform in nature. Instruct patient to report any rash immediately.
- Cytopenias can be seen. Monitor CBC w/diff closely. Instruct patient to report any signs or symptoms of infection and/or unusual bruising or bleeding to the study team.
- Bleeding including serious and/or fatal hemorrhage can be seen. Instruct patient to report any bleeding to study team.
- Monitor LFT's.
- Rarely interstitial lung disease can be seen. Instruct patient to report any cough, dyspnea to the study team.
- Rhabdomyolysis is a rare but serious side effect of this agent. Instruct patients to report any weakness, muscle pain, or just feelings or unwellness to the study team immediately.
- Instruct patient that it is important to only take agent on days 1-21 of the cycle. If any days in the 21 days are missed, they should not be made up and patients should cease taking agent on day 21.
- Rarely ocular complications can occur, including chorioretinopathy, retinal detachment and other visual disturbances. Instruct patients to report any visual disturbances and/or eye pain to the study team immediately.
- In combination with vemurafenib, patients may experience pyrexia. Instruct patients to report any fever or chills to the study team.

**11.0 MEASUREMENT OF EFFECT**

Response and progression will be evaluated in this study using the criteria specified below. Volumetric criteria by central radiology review will be used for assessment of the primary endpoint. Bidimensional area will be used locally for making about whether to proceed with treatment as per modified RANO guidelines.

**Imaging consistency monitoring rule:** After 10 enrollments to the study, central imaging review will be performed to evaluate for discordance between local imaging review and central imaging review. See [Section 13.5.3](#) for details.

**11.1 Schedule of evaluations:**

For the purposes of this study, patients should be reevaluated with MRI every 2 cycles. See [Section 5.0](#) for further details. Supporting documentation should be submitted as per [Section 6.1.1](#) and images submitted as per [Section 6.3](#).

**11.2 Definitions of measurable and non-measurable disease****11.2.1 Measurable disease**

Bidimensionally measurable lesions with clearly defined margins by MRI scans, with a minimum diameter of 10mm in both dimensions. Necrosis or cystic changes (nonenhancing disease) should be measured separately from and summed with contrast enhancing disease for measurements of tumor area.

### 11.2.2 Non-measurable disease

Unidimensionally measurable lesions, masses with margins not clearly defined.

## 11.3 Guidelines for evaluation of measurable disease

### 11.3.1 Measurement methods:

- All measurements should be recorded in metric notation (i.e., decimal fractions of centimeters) using a ruler or calipers.
- The same method of assessment and the same technique must be used to characterize each identified and reported lesion at baseline and during follow-up.

### 11.3.2 Acceptable modalities for measurable disease:

- **Conventional CT and MRI:** This guideline has defined measurability of lesions on CT scan based on the assumption that CT slice thickness is 5 mm or less. CT slice thickness of > 5 mm is not allowed. CT should ONLY be used for patients unable to undergo MR imaging because of non-compatible device or life-threatening gadolinium allergy.

MRI should be acquired as outlined in [Appendix II](#). The lesions should be measured on the same pulse sequence. Ideally, the same type of scanner should be used and the image acquisition protocol should be followed as closely as possible to prior scans.

### 11.3.3 Measurement at follow-up evaluation:

- A subsequent scan must be obtained 4 weeks following initial documentation of an objective status of either complete response (CR) or partial response (PR) for confirmation of response.
- In the case of stable disease (SD), follow-up measurements must have met the SD criteria at least once after study entry at a minimum interval of 8 weeks (see [Section 11.4.5](#)).

## 11.4 Measurement of treatment/intervention effect

### 11.4.1 Measurable lesions

Bidimensionally enhancing measurable lesions with clearly defined margins by MRI or CT scan. Necrosis or cystic changes (nonenhancing disease) should be measured separately from and summed with contrast enhancing disease for measurements of tumor area (unlike with glial tumors under RANO, given a different significance in craniopharyngioma).

A maximum of 1 target lesion should be followed.

### 11.4.2 Non-measurable lesions

Non-measurable sites of disease ([Section 11.2.2](#)) should also be recorded at baseline. These lesions should be followed in accord with [Section 11.4.5.1](#).

### 11.4.3 Target Lesions

Measurable lesions should be identified as target lesions and recorded and measured (sum of the products of the perpendicular diameters) at baseline. As compared to traditional RANO, target lesions will encompass both enhancing and cystic components of the tumor as the area of these lesions will be combined to summate the entire tumor area. Target lesion components should be selected on the basis of their size (lesions with the longest diameters) and their suitability for accurate repeated measurements by imaging techniques.

#### 11.4.4 Non-Target Lesions

For patients with recurrent disease who have multiple lesions of which only one or two are increasing in size, the enlarging lesions should be considered the target lesions for evaluation of response. The other lesions will be considered non-target lesions and should also be recorded. Rarely, unequivocal progression of a non-target lesion requiring discontinuation of therapy, or development of a new contrast-enhancing lesion may occur even in the setting of stable disease (SD) or partial response (PR) in the target lesions. These changes would qualify as progression. Non-target lesions also include measurable lesions that exceed the maximum number of 5. Measurements of these lesions are not required but the presence or absence of each should be noted throughout follow-up.

#### 11.4.5 Response criteria

**11.4.5.1** All measurable lesions followed by CT/MRI must be measured on re-evaluation at evaluation times specified in [Section 11.1](#). Specifically, a change in objective status to either a PR or CR cannot be done without re-measuring measurable lesions.

Note: Non-measurable lesions should be evaluated at each assessment, especially in the case of first response or confirmation of response.

##### 11.4.5.2 Evaluation of measurable lesions for local radiology review

- **Complete response (CR):** All of the following must be true:  
Disappearance of all measureable lesions on consecutive MRI or CT 4 weeks apart. No new lesions. No evidence of non-measurable disease. Lesions must be assessed using the same techniques at baseline. If [Appendix II](#) is not followed, imaging should continue per baseline acquisition parameters. Neurologically/clinically stable or improved. No corticosteroids for vasogenic edema.
- **Partial response (PR):**  
≥ 50% decrease under baseline in the sum of products of perpendicular diameters all enhancing, necrotic and cystic measurable components. No progression of nonmeasurable disease. No new lesions. All measurable and non-measurable lesions and sites must be assessed using the same techniques as baseline. If [Appendix II](#) is not followed, imaging should continue per baseline acquisition parameters. Neurologically/clinically stable or improved. Stable or reduced corticosteroid dose for vasogenic edema.
- **Progression (PD):** At least one of the following must be true:  
> 25% increase in the sum of products of all measurable lesion components (including enhancing, necrotic and cystic components) over smallest sum observed (over baseline if no decrease) using the same techniques as baseline. OR clear worsening of any nonmeasurable disease, OR appearance of any new lesion/site, OR clear clinical worsening or failure to return for evaluation due to death or deteriorating condition (unless clearly unrelated to this cancer)  
>25% increase in the sum of products of all measurable lesion components (including enhancing, necrotic and cystic components) but < 50% increase in the sum of products of all measurable lesion components (including enhancing, necrotic and cystic components) AND no new lesions/sites in scans obtained AND no clear clinical deterioration: When all of these conditions are met, the patient may continue on drug for 4 weeks. Imaging must be repeated 4 weeks later

(+/- 7 days). If imaging at 4 weeks shows continued growth of greater than 25%, then patient has definitive progression and date of progression should be back dated to the first MRI where there was a >25% increase.

- **Stable disease (SD):** Neither sufficient shrinkage to qualify for PR, nor sufficient increase to qualify for PD taking as reference the MSD. Stable clinically

#### 11.4.5.3 Evaluation of non-measurable lesions for local review

- **Complete response (CR):** Disappearance of all non-measurable lesions.
- **Stable disease (SD):** Persistence of one or more non-measurable lesions.
- **Progression (PD):** Unequivocal progression of existing non-measurable lesions (NOTE: Unequivocal progression should not normally trump measurable lesion. It must be representative of overall disease status change.)

#### 11.4.5.4 Evaluation of measurable lesions for central radiology review

Criteria for central radiology review is based on volumetric criteria that has been used in other brain tumors, including benign brain tumors.

- **Complete response (CR):** All of the following must be true:  
Disappearance of all measurable lesions on consecutive magnetic resonance imaging (MRI) or CT 4 weeks apart. No new lesions. No evidence of non-measurable disease. Lesions must be assessed using the same techniques at baseline. Neurologically/clinically stable or improved
- **Partial response (PR):**  
≥20% decrease under baseline in the volume of all measurable lesions. No progression of nonmeasurable disease. No new lesions. All measurable and non-measurable lesions and sites must be assessed using the same techniques as baseline. Neurologically/clinically stable or improved
- **Progression (PD):** At least one of the following must be true:  
> 20% increase in the volume of all measurable lesions using the same techniques as baseline, OR clear worsening of any nonmeasurable disease, OR appearance of any new lesion/site, OR clear clinical worsening or failure to return for evaluation due to death or deteriorating condition (unless clearly unrelated to this cancer)
- **Stable disease (SD):** Neither sufficient shrinkage to qualify for PR, nor sufficient increase to qualify for PD. Stable clinically

#### 11.4.5.5 Evaluation of non-measurable lesions for central radiology review

- **Complete response (CR):** Disappearance of all non-measurable lesions.
- **Non-CR/Non-PD:** Persistence of one or more non-measurable lesions.
- **Progression (PD):** Unequivocal progression of existing non-measurable lesions (NOTE: Unequivocal progression should not normally trump measurable lesion. It must be representative of overall disease status change.)

#### 11.4.5.6 Evaluation of volumetric vs. two-dimensional tumor measurements

A correlation between volumetric and two-dimensional tumor measurements and their relative changes with relevant patient outcomes will be made through central radiology review, in order to determine whether there exist any advantages in volumetric tumor measurements over two-dimensional tumor measurements.

#### 11.4.6 Overall objective status

The overall objective status for an evaluation is determined by combining the patient's status on measurable and nonmeasurable disease, and new disease as defined in the following tables:

For Patients with Measurable Disease

Summary of the Modified RANO Response Criteria Table

	CR	PR	SD	PD 
Target Lesion (Sum of Products of Enhancing, Necrotic, and Cystic Measureable Components)	None	$\geq 50\%$ decrease	$< 50\%$ decrease to $< 25\%$ increase	$\geq 25\%$ increase*
Non-target Lesion Sites	Stable or decrease	Stable or decrease	Stable or decrease	Increase* 
New Lesion	None	None	None	Present*
Corticosteroids	None	Stable or decrease	Stable or decrease	NA
Clinical Status	Stable or improved	Stable or improved	Stable or improved	Worsened*
Requirement for Response	All	All	All	Any*

CR = complete response; PR = partial response; SD = stable disease; PD = progressive disease

\* Progression occurs when any of the criteria with \* are present

 This is considered PD if the increase in a nontarget lesion is felt likely to represent tumor progression.

NA – Increase in corticosteroids alone will not be taken into account in determining progression in the absence of persistent clinical deterioration

**11.4.7 Symptomatic neurologic deterioration:** Patients with global deterioration of health status requiring discontinuation of treatment without objective evidence of disease progression at that time, and not either related to study treatment or other medical conditions, should be reported as PD due to “symptomatic deterioration.” Every effort should be made to document the objective progression even after discontinuation of treatment due to symptomatic deterioration.

A patient is classified as having PD due to “symptomatic deterioration” if any of the following occur that are not either related to study treatment or other medical conditions:

- Worsening of neurologic examination.
- Worsening of tumor-related and/or neurologic symptoms.
- Decline in performance status of >1 level on ECOG scale.
- Increase in seizure frequency or severity lasting > 14 days

## **11.5 Definitions of analysis variables**

Formal definitions of variables used in analyses can be found in the Statistical Considerations section of the protocol.

## 12.0 END OF TREATMENT/INTERVENTION

### 12.1 Duration of treatment

**12.1.1 CR, PR, or SD:** Patients who are in CR, PR or SD will continue on therapy as outlined below:

- Cohort A: Patients can continue on therapy for a total of 4 cycles in cohort A, and then go on to receive radiation, surgery or both as outlined in [Section 7.1.1](#). In special circumstances, continuation of therapy with vemurafenib and cobimetinib may be granted, but only with approval from the radiation oncology chair (see [Section 7.1.1](#) for additional details). If continuation is approved, then therapy with cobimetinib and vemurafenib can continue until documented progression, unacceptable adverse events, or drug hold >28 days.
- Cohort B: Patients can continue therapy with cobimetinib and vemurafenib until documented progression, unacceptable adverse events, or drug hold >28 days (see [Section 7.1.2](#)). After treatment is completed or discontinued, patients will be followed per the study calendar in [Section 5.0](#).

**12.1.2 Disease progression:** Remove from protocol therapy any patient with disease progression. Document details, including tumor measurements, on data forms.

After disease progression, patients should be followed for survival per the study calendar ([Section 5.0](#)).

**12.1.3 Discontinuation of study agent:** If the patient discontinues protocol therapy due to reasons other than PD (i.e. for unacceptable adverse events, drug hold >28 days), prior to the completion of planned therapy as per [Section 7.0](#), patients should go on to clinical and survival follow up per the study calendar ([Section 5.0](#)). This includes:

- Patients who discontinue treatment before the end of 4 cycles of treatment to begin alternative therapy.
- Patients who discontinue continued treatment with vemurafenib and cobimetinib to begin alternative therapy (i.e. patients on Cohorts A or B who choose to continue therapy with vemurafenib and cobimetinib post the initial 4 cycles).

**12.1.4 Discontinuation of study agent in patients with expected AEs:** See [Section 8.2.4](#) for more information.

### 12.2 Managing ineligible patients and registered patients who never receive protocol intervention

#### Definition of ineligible patient

A study participant who is registered to the trial but does not meet all of the eligibility criteria is deemed to be ineligible.

#### Follow-up for ineligible patients who continue with protocol treatment

Patients who are deemed ineligible after registering may continue protocol treatment, provided the treating physician, study chair, and executive officer agree there are no safety concerns if the patient continues protocol treatment. All scans, tests, and data submission are to continue as if the patient were eligible. Notification of the local IRB may be necessary per local IRB policies.

#### Follow-up for ineligible patients who discontinue protocol treatment

For patients who are deemed ineligible after registering to the trial, who start treatment, but then discontinue study treatment, the same data submission requirements are to be followed as for those patients who are eligible and who discontinue study treatment.

**Follow-up for patients who are registered, but who never start study treatment**

For all study participants who are registered to the trial but who never receive study intervention (regardless of eligibility), the follow-up requirements are specified below.

Baseline and off-treatment notice data submission required. See the Data Submission Schedule accompanying the All Forms Packet.

**12.3 Extraordinary medical circumstances**

If, at any time the constraints of this protocol are detrimental to the patient's health and/or the patient no longer wishes to continue protocol therapy, protocol therapy shall be discontinued. In this event:

- Document the reason(s) for discontinuation of therapy on data forms.
- Follow the patient for protocol endpoints as required by the Study Calendar.

## 13.0 STATISTICAL CONSIDERATIONS

### 13.1 Study design

This is a prospective, single-arm phase 2 study evaluating the efficacy of BRAF and MEK inhibitor combination in patients with papillary craniopharyngiomas. The primary endpoint of response rate (RR) while being treated with BRAF and MEK inhibitors will be evaluated in two cohorts, separately, i.e., newly diagnosed patients (untreated cohort) and patients who have progressed after prior radiation treatment with or without surgical resection (recurrent cohort). The statistical design is the same for each cohort. Simon's two-stage design with one interim analysis for futility will be applied to evaluate RR within each cohort. The accrual will not be halted at the interim analysis unless the accrual is too rapid.

### 13.2 Statistical design and analysis for the primary endpoint

#### 13.2.1 Primary endpoints

The primary end point is response rate (RR), defined as the number of responses achieved during treatment with BRAF and MEK inhibitors divided by the total number of evaluable patients. For the recurrent cohort, only responses achieved during the first four cycles of treatment with BRAF and MEK inhibitors will count toward the primary endpoint. A patient will be deemed to have a response if CR or PR measured by central radiologic review (see [Section 11.4.5.4](#) and [11.4.5.5](#)) is achieved. Contrast-enhanced magnetic resonance imaging (MRI) or CT will be performed every 2 cycles with volumetric assessment.

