## **2.0 OBJECTIVES**

### **2.1 Co-primary objectives**

- 2.1.1** To determine the activity of BRAF and MEK inhibitor combination in untreated papillary craniopharyngiomas as measured by best response at any time during the first four cycles of BRAF and MEK inhibitor treatment.
- 2.1.2** To determine the activity of BRAF and MEK inhibitor combination in papillary craniopharyngiomas that have progressed after prior radiation treatment with or without surgical resection as measured by best response at any time during the first four cycles of BRAF and MEK inhibitor treatment.

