#### 7.1.1 Cohort A

For Cohort A, patients should receive treatment for up to 4 cycles with vemurafenib + cobimetinib (unless progression, unacceptable toxicity, or patient withdrawal from study occurs). See [Section 12.0](#) for additional information. After 4 cycles of vemurafenib and cobimetinib, surgery or radiation for definitive therapy should be performed. Continuation of vemurafenib and cobimetinib beyond 4 cycles in cohort A will require approval from the radiation oncology chair and study chair. If patient stays on study for longer than 4 cycles, visits and labs at the beginning of every cycle are still required with scans every 2 cycles, as per the study calendar.

- **For patients that achieve CR**, they will undergo definitive radiation.
- **For patients with any response that is not CR or better**, the decision of therapy between surgery, or radiation, or both, is at the discretion of the treating physician.

**For patients who go on to receive radiation**, the pre-treatment scan would be used as a guide for radiation planning. See [Section 7.2](#) for radiation guidelines. Vemurafenib and cobimetinib need to be stopped at least two weeks prior to initiation of radiation therapy. For purposes of radiation planning, if duration of BRAF/MEK inhibitor treatment needs to be extended this will be allowed, for a maximum length of 4 additional weeks (i.e., 5 cycles maximum).

**In special cases**, if radiation or surgery are not recommended for the patient because of potential risks, then the patient may continue on cobimetinib and vemurafenib past 4 cycles, until disease progression or unacceptable adverse events. **However, continuation of treatment can only be granted with approval from the radiation oncologist and study chair.** A request, with accompanying rationale, must be sent to the radiation oncologist and protocol coordinator. Approval must be obtained via email prior to Cycle 5 drug shipment. The email containing the approval must also be submitted via Rave as supporting documentation.

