### 13.4 Supplementary analysis plans

#### 13.4.1 Secondary Endpoints

- **Progression free survival:** progression free survival (PFS) will be estimated using the C Kaplan-Meier method within each cohort. Median PFSs and survival rates will be estimated with their 95% confidence intervals. No formal comparison will be made among the cohorts.
- **Toxicity:** As per NCI CTCAE v 4.0, the term toxicity is defined as adverse events that are classified as possibly, probably, or definitely related to study treatment. Toxicities will be evaluated via the ordinal CTCAE standard toxicity grading. Overall toxicity incidence as well as toxicity profiles by patient and treatment cohort will be explored and summarized. Frequency distributions, graphical techniques and other descriptive measures will form the basis of the analysis. No formal comparison will be made among the cohorts.
- **Response as defined by Enhancing Volume:** Response by Enhancing Volume will be estimated using Response Rate (RR) - where response rate is defined as the number of responses achieved during treatment with BRAF and MEK inhibitors divided by the total number of evaluable patients. For this endpoint, only decreasing volume in enhancing disease will count toward the criteria for response. The same thresholds for CR and PR as seen in Section 11.0 will be used. Point estimates will be generated for response rates within each cohort with corresponding 95% binomial confidence intervals (Duffy and Santner).
- **Response as defined by Non-Enhancing Volume:** Response by Non-Enhancing Volume will be estimated using Response Rate (RR) - where response rate is defined as the number of responses achieved during treatment with BRAF and MEK inhibitors divided by the total number of evaluable patients. For this endpoint, only decreasing volume in non-enhancing disease will count toward the criteria for response. The same thresholds for CR and PR as seen in [Section 11.0](#) will be used.

Point estimates will be generated for response rates within each cohort with corresponding 95% binomial confidence intervals (Duffy and Santner).

- **Overall Survival:** overall survival (OS) will be estimated using the Kaplan-Meier method within each cohort. Median overall survivals and survival rates will be estimated with their 95% confidence intervals. No formal comparison will be made among the cohorts.

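### The primary endpoint applies the four-cycle response window only to the recurrent cohort, although the co-primary objective sets the same window for untreated Cohort A

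*Combined protocol and SAP*

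**What the plan says.** Section 2.1 states two co-primary objectives with the same time window. For Cohort A, activity is assessed "in untreated papillary craniopharyngiomas as measured by best response at any time during the first four cycles" of treatment. For Cohort B, it is assessed in patients previously irradiated, "with or without surgical resection as measured by best response at any time during the first four cycles of BRAF and MEK inhibitor treatment".

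Section 13.2.1 turns these objectives into an endpoint. The response rate is "defined as the number of responses achieved during treatment with BRAF and MEK inhibitors divided by the total number of evaluable patients". The next sentence adds a limit: "For the recurrent cohort, only responses achieved during the first four cycles of treatment" count. No sentence in Section 13 places a limit on Cohort A.

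On treatment length, Section 7.1.1 gives the default: "For Cohort A, patients should receive treatment for up to 4 cycles with vemurafenib + cobimetinib". It then allows two extensions. One is a single extra cycle for radiation planning. The other covers special cases in which radiation or surgery is not advised: "then the patient may continue on cobimetinib and vemurafenib past 4 cycles, until disease progression or unacceptable adverse events". The second needs approval before Cycle 5 drug is shipped. Section 12.1.1 and the schema footnotes also provide for continuation. Patients who stay on treatment keep the two-cycle scan schedule.

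Section 13.2.3 runs the interim and final analyses once the 9th and 16th evaluable patients are off treatment. Accrual continues with at least 1 response in 9, and activity is declared with at least 3 in 16.

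**The concern.** The same Cohort A patient can be classified in two ways. Someone on approved extension who first meets the volumetric partial-response threshold after cycle 4 is a responder under 13.2.1 and a non-responder under 2.1.1. The protocol has no rule on which text governs. Because the limit names one cohort, the natural reading is that the other has none.

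Three things are at stake. Different counts could lead to different conclusions about Cohort A. The choice between them could be made after the responses are known. And a longer window can only add responses, whereas the stated error rate assumes a 5% response probability under the null.

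**Working it through.** **1. The plan's own figures.** Inputs from Sections 13.2.2 and 13.2.3: n1 = 9, continue with ≥1 response; n = 16, success with ≥3; null rate 5%, alternative 30%.

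P(success) = Σ over x ≥ 1 of Bin(9, p)(x) × P(Bin(7, p) ≥ 3 − x). P(stop at stage 1) = (1 − p)^9.

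| True rate | P(success), computed / plan | P(stop), computed / plan |
|---|---|---|
| 0.05 | 0.0406 / 0.041 | 0.6302 / 0.630 |
| 0.10 | 0.2008 / 0.201 | 0.3874 / 0.387 |
| 0.30 | 0.8864 / 0.886 | 0.0404 / 0.040 |

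The family-wise rate is 1 − (1 − 0.0406)² = 0.0795, stated as 0.08. The plan's figures reproduce. None of them depends on how the window is worded, provided the 5% null applies to the window actually used.

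**2. The two definitions side by side.**

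| Cohort A patient | Objective 2.1.1 | Section 13.2.1 |
|---|---|---|
| Response first seen within cycles 1–4 | counts | counts |
| Extended by approval; response first seen after cycle 4, on drug | does not count | counts |

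**3. Which extensions can add a scan.** Scans fall every two cycles. After the cycle-4 assessment the next scheduled one is at cycle 6, so the radiation-planning extension (five cycles at most) adds no scheduled every-two-cycle scan. The approved special-case extension does.

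**4. How often one response is decisive.** A cohort passes stage 1 and ends with exactly 2 responses with probability Bin(16, p)(2) − Bin(9, p)(0) × Bin(7, p)(2).

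- At 5%: 0.1463 − 0.6302 × 0.0406 = 0.121.
- At 10%: 0.2745 − 0.3874 × 0.1240 = 0.226.

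In those outcomes one more response reverses the conclusion. At stage 1, no response in 9 has probability 0.630 at the 5% null, and one response turns stopping into continuing. These are the probabilities of standing on the edge. They are not the probability that a late response occurs.

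**5. Possible size (assumptions, not in the documents).** Let the null rate be 5% within four cycles, let a share f of the other patients be extended, and let a share q of those respond late. The effective null rate is 0.05 + 0.95·f·q.

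| f | q | Effective rate | Cohort A type I error |
|---|---|---|---|
| 5% | 5% | 0.0524 | 0.046 |
| 10% | 10% | 0.0595 | 0.062 |
| 20% | 10% | 0.0690 | 0.089 |

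A second illustration assumes no true change and only volume-measurement error, with the baseline error shared across scans. At an assumed coefficient of variation (CV) of 8%, the chance that at least one scan is at or below 80% of baseline is 0.0437 with two scans and 0.0605 with three. If one of 16 patients reaches six cycles, the average is 15/16 × 0.0437 + 1/16 × 0.0605 = 0.0448, and P(success) moves from 0.029 to 0.031. At a CV of 5% the effect is negligible.

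**The case against.** The strongest reply is that Cohort A stops at four cycles anyway, so 13.2.1 needed to name only the cohort that routinely continues. That is probably how the wording arose, although the documents do not say so, and it explains why the reach is narrow. It does not remove the conflict: four cycles is the default, and Sections 7.1.1 and 12.1.1 provide for treatment until progression.

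Three stronger readings are tempting and are not supported.

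- A reader might infer that the type I error is badly inflated. Large figures need a large extended share, which the documents do not give and which sits poorly with an approval-only exception. They may also need a high measurement error. At an assumed CV of 10%, P(success) is already about 0.20 with the four-cycle limit in force, so that excess comes from noise against a 20% threshold and not from the missing window. These calculations also count single scans. Section 11.3.3 calls for a confirmation scan, which would lower them if confirmation is needed to count; the central-review definition of partial response does not state that requirement.
- A reader might infer that the enhancing and non-enhancing response rates in Section 13.4.1 are inconsistent because they carry no window. Objectives 2.2.3 and 2.2.4 set none, so objective and analysis agree there.
- A reader might want a fixed calendar cut-off for the end of cycle 4. Scans are timed from the baseline scan, cycles may start up to 7 days late, and a drug may be held for up to 28 days. A fixed day could exclude a genuine end-of-Cycle-4 assessment.

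**Conclusion.** The mismatch between objective 2.1.1 and Section 13.2.1 is real and rests on the text alone. It affects only Cohort A patients treated past cycle 4, in practice those with approved special-case continuation. Their number is not given and is probably small, so the effect on the 0.041 error rate is likely small. The illustrations in the working run from almost no change to 0.089, depending wholly on the assumed extension rate, late-response rate and measurement error. What gives the point weight is the decision rule: with thresholds of 1 in 9 and 3 in 16, a single late response can change either decision. The correction should be made, but the design does not fail without it.

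**What to change.** In Section 13.2.1, replace the sentence beginning "For the recurrent cohort, only responses achieved during the first four cycles of treatment" with:

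*In both cohorts, only responses first documented on or before the scheduled end-of-Cycle-4 tumor assessment (with its protocol window, and defined by cycle rather than by a fixed calendar day), and before any surgery or radiation, count toward the primary endpoint; later responses are reported descriptively.*

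This brings the analysis into line with objectives 2.1.1 and 2.1.2 and settles the status of the cycle-4 scan. The cost is one sentence. Sample size, decision rules, alpha, power and patient treatment stay as they are. The downside is that an occasional late Cohort A response no longer counts toward the primary endpoint, although it is still reported.
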